#### **6.4. Medical History**

Medical History will be coded using the Medical Dictionary for Regulatory Activities (MedDRA) and summarized by system organ class (SOC) and Preferred Term using frequency counts and percentages by treatment group. Nasal Exam findings will be summarized using frequency counts and percentages by treatment group. Physical examination and nasal exam findings will be presented in listings.

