# Efficacy Mean change from Baseline in the Migraine Disability Assessment (MIDAS) Test total score at Week 12. Secondary **Endpoints:** Mean change from Baseline in the Hospital Anxiety and Depression Scale (HADS) total score at Week 12. Mean change from Baseline in patient-rated Changes in Sexual Functioning Questionnaire Short-Form (CSFQ-14) total score in males and in females, analyzed separately, at Week 12. **Exploratory** Proportion of patients experiencing a $\geq$ 75% reduction in the number of **Endpoints:** migraine headache days from the last 28 days of Baseline to the last 28 days of treatment in each treatment group. • Proportion of patients with fewer than 14 headache days or fewer than 8 migraine headache days per 4 weeks over the 12-week period. Mean change from Baseline in number of headache free days from the last 28 days of Baseline to the last 28 days of treatment. • PGIC rating (1-7) at Week 12 Safety Change in suicidality using the C-SSRS scale **Endpoints:** Incidence of adverse events (AEs) Changes from Baseline in clinical laboratory tests • Changes from Baseline in vital signs Change from Baseline in ECG parameters Clinically significant change(s) in physical examination findings Clinically significant change(s) in nasal examination findings Changes from Baseline in the Hospital Anxiety and Depression Scale (HADS) total score at Week 12 Changes from Baseline in patient-rated Changes in Sexual Functioning Questionnaire Short-Form (CSFQ-14) in males and in females, described separately The modified intention-to-treat population (mITT), defined as all randomized Statistical patients who receive at least 1 dose of study drug and have at least one post-Methods: Baseline, evaluable month (that is, at least one of the three 28-day periods has at least 14 non-missing e-diary entries), will be used as the primary population for all efficacy analyses. The sample size and power calculations for this study are based on the analysis of the primary efficacy outcome variable: mean change in the number of migraine headache days from the last 28 days of Baseline to the last 28 days of treatment in each treatment group. **Efficacy Analysis** The primary efficacy endpoint of change from Baseline will be analyzed using a mixed-effects model of repeated measures (MMRM) with fixed

effects of treatment, month, baseline value, treatment by month interaction,

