#### 6.4 Nasal Examination

A nasal examination will be performed at Visit 1, Visit 2, Visit 3, Visit 4, and Visit 5. The nasal exam will be conducted using a nasal speculum and headlamp to view into each nostril in order to establish any baseline pathology and assess any clinically significant changes in the nasal passages. A nasal exam should only be conducted at Visit 6 if needed to follow up on unresolved findings from the Visit 5 examination.

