## **8. GENERAL ANALYSIS AND REPORTING CONSIDERATIONS**

Descriptive summaries will be provided where appropriate for each of the primary and secondary variables. In general, tables will summarize data by treatment group and visit.

Continuous, quantitative variable summaries will include the number of patients (N) with non-missing values, mean, standard deviation, median, minimum, and maximum.

Categorical, qualitative variable summaries will include the frequency and percentage of patients who are in the particular category. In general, the denominator for the percentage calculation will be based upon the total number of patients in the study population for the treatment group unless otherwise specified.

Unless otherwise specified, baseline values are defined as the last non-missing measurement prior to the first dose of study drug. Change from baseline will be defined as the post-baseline visit value minus the baseline value.

For continuous endpoints where treatment groups are compared via linear models with the difference in LS means, the effect size will be calculated and included as a summary statistic using the difference in LS means and its standard error, transformed to a standard deviation. Study day is defined as assessment date – first dose date +1 for dates after the first dose date and assessment date – first dose date for dates prior to the first dose.

All analyses will be performed using SAS® Software version 9.4 or later.

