## 10. SAFETY EVALUATION

### 10.1. Overview of Safety Analysis Methods

All safety analyses will be completed for the Safety Population. All safety data will be tabulated and listed. No formal statistics or imputation will be performed for the safety analysis. The analysis of safety assessments in this study will include summaries of the following safety and tolerability data collected for each patient:

- Extent of exposure
- Incidence of Adverse Events
- Changes from baseline in clinical laboratory results
- Changes from baseline in vital signs
- Changes from baseline in electrocardiograms
- Monitoring suicidality using the Columbia Suicide Severity Rating Scale (C-SSRS)
- Changes from baseline in the HADS scores
- Changes from baseline in the CSFQ-14

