## **10.5. Clinical Laboratory Evaluation**

Laboratory data including Chemistry, Hematology, and urinalyses will be summarized by treatment and visit for the Safety Population. Descriptive summaries of actual values and changes from baseline will be presented by study visit and last assessment for each clinical laboratory analyte and for each treatment group. 95% confidence intervals will be presented for change from baseline.

Laboratory values will be displayed in the data listings with their corresponding normal ranges, and those values that are outside the normal range will be flagged. For each laboratory analyte shifts in assessments of abnormality from baseline to each scheduled time point will be presented in shift tables.

Results of urine drug screens and pregnancy tests will be presented in listings.

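### The SAP plans no change-from-baseline analysis of the nasal examination, which the protocol lists as a safety endpoint; its one nasal-exam table, under Medical History, can show prevalence at most

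*SAP*

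**What the plan says.** **Protocol.** The synopsis safety endpoints include "Clinically significant change(s) in nasal examination findings", listed separately from the incidence of adverse events (AEs). Section 6.4 sets the schedule: "A nasal examination will be performed at Visit 1, Visit 2, Visit 3, Visit 4, and Visit 5". It says the examination is done "in order to establish any baseline pathology and assess any clinically significant changes in the nasal passages". Visit 6 has a conditional repeat only. Section 6.9 counts the nasal exam among the safety assessments. Section 7.2.8.1 makes nasal irritation an AE of special interest (AESI) and asks investigators to look for mucosal lesions on examination.

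**SAP.** Section 6.4, Medical History, has two relevant sentences: "Nasal Exam findings will be summarized using frequency counts and percentages by treatment group" and "Physical examination and nasal exam findings will be presented in listings". Section 10.1 opens its list with "The analysis of safety assessments in this study will include summaries of the following safety and tolerability data collected for each patient". The items are exposure, AEs, laboratory results, vital signs, ECG, C-SSRS, HADS and CSFQ-14; the nasal exam is not among them. Sections 10.5 and 10.6 do not mention it either. Section 10.4 covers nasal cavity AEs but not examination findings as such. Section 8 gives a general rule: "In general, tables will summarize data by treatment group and visit".

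**The concern.** The protocol endpoint is a change, and the examination is repeated so that change can be seen. The SAP's table names no baseline comparison, no visit, no category of clinical significance and no analysis population. It sits in a section that describes patients at entry.

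Baseline nasal findings can be expected. Exclusion 16 removes chronic obstruction or local pathology only where the investigator judges that it would prevent proper dosing. Exclusion 14 removes patients who use, or may need, intranasal corticosteroids. Milder findings can still enter the trial. Without a baseline reference, an abnormality present before the first dose and one that appears on treatment are the same kind of entry.

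For a product sprayed into the nose twice a day, the examination is the direct observation of the site of administration. At stake is whether the study report contains a summary by arm of the local-tolerability endpoint that the protocol names.

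**Working it through.** No figure in the documents bears on this point, so the check is mainly a comparison of texts.

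**1. Is there a change analysis anywhere?** SAP 10.5 promises for laboratory analytes that "shifts in assessments of abnormality from baseline to each scheduled time point will be presented in shift tables". SAP 10.6.2 tabulates ECG interpretation by category at each time point. SAP 10.6.3 gives physical examination a listing only. No SAP section defines a shift, a change or a clinically significant category for the nasal exam. Protocol 10.5.1 and 10.7.3 give no method for it either, and Protocol 10.1 leaves further methodological detail to the SAP.

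**2. What can the 6.4 sentence mean?**

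| Reading | Basis | Shows within-patient change? |
|---|---|---|
| Baseline only | its place under Medical History | No; no post-baseline table exists |
| By arm and visit | the default in SAP 8 | No; prevalence at each visit |
| All visits pooled | the sentence taken alone | No; old and new findings are mixed |

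The endpoint is not tabulated under any of the three. Prevalence by visit can hide turnover. Suppose 15 of 100 patients have a finding at Visit 2, 8 of those clear, and 8 other patients develop one. Prevalence afterwards is 15 − 8 + 8 = 15 of 100, unchanged, although 8 patients have a new finding. (These counts are assumed.)

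**3. How large could dilution be?** This is an illustration and every rate is assumed. Let b be the share of patients with a pre-existing finding that persists, equal in both arms. Let q be the rate of new findings among the rest: 10% on active, 2% on placebo. Counting new findings only gives a ratio of 10 / 2 = 5.0. Counting any finding gives b + (1 − b)q:

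| b | Placebo | Active | Ratio |
|---|---|---|---|
| 10% | 0.10 + 0.90 × 0.02 = 11.8% | 0.10 + 0.90 × 0.10 = 19.0% | 1.61 |
| 20% | 0.20 + 0.80 × 0.02 = 21.6% | 0.20 + 0.80 × 0.10 = 28.0% | 1.30 |
| 30% | 0.30 + 0.70 × 0.02 = 31.4% | 0.30 + 0.70 × 0.10 = 37.0% | 1.18 |

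Under the by-visit reading, a Visit 2 column would stand beside these figures. A reader could then subtract it, for example 19.0 − 10 = 9.0%, but this equals the new-finding rate in the whole arm only if nothing resolves. The dilution therefore applies in full only to a pooled table.

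**4. Do new lesions appear elsewhere?** Yes, largely. Protocol 7.2.1 treats clinically relevant observations at a visit as AEs. Protocol 7.1 leaves out pre-existing conditions unless they worsen. SAP 10.3 requires onset or worsening after the first dose for an event to be treatment-emergent. SAP 10.4 has nasal cavity AEs identified on the CRF, tabulated and listed. That route has its own baseline reference, so step 3 does not apply to it.

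**The case against.** The strongest reply has four parts.

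- **The default layout.** SAP 8 makes tables by arm and visit in general, and SAP 10.1 says all safety data are tabulated and listed. The nasal table may therefore be by visit. This stands: the sentence is ambiguous, not clearly pooled. A by-visit prevalence table is still not a change analysis.
- **The AE route.** A reader might infer that the 6.4 table hides new mucosal lesions, or that the trial will be unable to report on local tolerability. The documents do not support either inference. Step 4 shows that clinically relevant new or worsened findings should reach the AE and AESI tables undiluted, and SAP 6.4 lists every examination finding. What remains is narrower. The synopsis names AEs and examination change as separate endpoints, and the AESI in Protocol 7.2.8.1 covers pain and discomfort as well as lesions seen on examination.
- **Unequal comparison.** ECG interpretation has no shift table, and physical examination, whose change is also a synopsis endpoint, gets only a listing. The nasal exam is not alone in this. Its claim to more rests on the route of administration and the AESI status that the protocol gives to nasal irritation.
- **Origin and redaction.** Protocol 10.5.1 and 10.7.3 do not carry the synopsis endpoint forward, so the gap begins there. SAP 13, on changes from the protocol, is redacted, so a stated reason cannot be ruled out. Neither point puts an analysis into the visible safety chapter.

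**Conclusion.** The point holds in limited form. The SAP's one stated method for nasal examination data cannot show within-patient change, however its sentence is read, and the safety chapter leaves the endpoint out. The loss is confined to the tabulated examination endpoint and to new or worsened findings that are not reported as AEs.

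Its size cannot be taken from the documents, which give no rate of baseline or new nasal findings. The ratios of about 1.2 to 1.6 rest on assumed rates, on persistence of pre-existing findings and on a table without a baseline reference. They show the direction of the effect and are not a forecast. The SAP plans no formal statistics for safety, so no test result depends on this. It should be corrected because the endpoint is named in the protocol, concerns the site of administration and costs little to summarise properly.

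**What to change.** 1. In SAP 6.4, keep only the description of nasal findings at baseline.
2. Add the nasal examination to the list in SAP 10.1 and give it a subsection in 10.6, on the Safety Population.
3. Specify a shift table by arm from the last examination before the first dose (normally Visit 2, consistent with the baseline rule in SAP 8) to Visits 3, 4 and 5 and to the worst post-baseline result. State whether the conditional Visit 6 examination counts towards the worst result.
4. Report by arm the number and percentage of patients with any new or worsened clinically significant nasal finding, with patients examined after baseline as the denominator.
5. Name the result categories. The CRF is not among the documents. If it does not record clinical significance for this examination, set a classification rule before unblinding.
6. Keep the nasal AE and AESI tables and the listing as they are.

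The cost is a few lines of SAP text and one or two tables from examinations already scheduled. No visit or procedure changes.

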## 7. STUDY OPERATIONS

### 7.1. Protocol Deviations

A protocol deviation is any noncompliance with the clinical trial protocol or ICH Good Clinical Practice (GCP) requirements. The noncompliance may be either on the part of the patient, the investigator, or the study site staff. As a result of deviations, corrective actions are to be developed by the site and implemented promptly. Protocol deviations will be logged and categorized as important or non-important prior to unblinding. Protocol deviations will be summarized by type, status as important or non-important, and by treatment group for the Safety population.

Individual protocol deviations will be listed by patient.

### 7.2. Randomization

This is a double-blind study; unless otherwise specified, all study personnel are to remain blinded to study drug prior to database lock and final analysis following study unblinding.

Approximately 300 eligible patients will be randomized at a 1:1:1 ratio, to one of the 3 treatment arms receiving TNX-1900 at a fixed daily dose of 30 IU QD (Treatment Arm A) or fixed daily dose of 30 IU BID (Treatment Arm B) or receiving placebo (Treatment Arm C) for the duration of a 12-week Treatment Period. Randomization will be stratified by site and use of one concomitant preventive migraine medication (vs. no concomitant preventive migraine medication). All participants will administer study drug twice a day, mornings and evenings, in a double-blind design. Up to approximately 30% of the patients randomized into the study can be on 1 migraine preventative medication.

The randomization schedule will be computer generated using a permuted block algorithm and will randomly allocate study drug to randomization numbers. The randomization numbers will be assigned through a central interactive web response system (IWRS) as patients are entered into the study.

### 7.3. Measures of Treatment Compliance

No direct measures of drug compliance will be captured via drug accountability. Compliance via the diary will be reported for the post-baseline period. Patients are asked to report whether they took their morning and evening doses; compliance will be reported as the number of “Yes” responses reported out of the total number of expected doses based on the dates the diary was issued and collected times 2 doses/day. The compliance will be summarized with descriptive statistics. Additionally, the number and percentage of patients with <70% compliance, 70% to <80%, 80% to <90%, and 90 to 100% compliance will be reported.

Additionally, compliance with diary completion will be reported and summarized with descriptive statistics. Diary compliance will be defined as the number of days which have ANY data entered (even if partial/incomplete) divided by the number of days they were expected to complete the diary. This will be summarized for the baseline and post-baseline periods separately.

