# Eligibility Criteria for Randomization:

Up to approximately 30% of the patients randomized into the study can be on 1 migraine preventative medication. Once this category is filled, only patients who are not on any preventative medications can be randomized into the study. From study start, sites should enroll patients into both categories in parallel until informed otherwise.

For a patient to be eligible for randomization, the following should be observed during the last 28 days of the Run-in Period:

- 1. Demonstrate an ability to properly use e-diary.
- 2. Complete  $\geq$  82% of the e-diary daily entries (at least 23 days out of the 28-day period).
- 3. At least 14 headache (migraine-like or tension-type-like) days
- 4. At least 8 days where the patient experiences any of the following:
  - An attack lasting 4 hours or more and meeting the ICHD-3 criteria (diagnostic criteria C and D) for migraine without aura (Appendix A)
  - Migraine with aura
  - Probable migraine (a migraine subtype fulfilling all but one criterion (B-D) for migraine without aura)
  - An attack of any duration that was believed by the patient to be a migraine and was relieved by a triptan, ergot derivative, or other migraine-specific abortive medication.

It is important to note that the last 28 days of Run-In diary entries includes diary entries logged on morning of the Baseline Visit. Patients should be reminded to complete the required e-diary entries on the morning of the Baseline Visit.

Patients may be withdrawn from the Run-in Period prior to the end of 28 days if patients are determined mathematically to be unable to meet the headache criteria required by the protocol.

Those patients who only miss the e-diary compliance requirement (i.e., compliance less than 82%) and otherwise are qualified for randomization may be given the opportunity to either extend or repeat the Run-in Period. Any extension will be considered on a case-by-case basis and require medical monitor approval.

At Baseline/Randomization/V2, patients must still meet all inclusion criteria and none of the exclusion criteria and be in good general health, or with only stable and non-serious conditions that, in the opinion of the investigator, will not place the patient at risk.

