### **4.2. Modified Intent-to-Treat Population**

The mITT population will include all randomized patients who received at least one dose of study drug and had at least one post-Baseline evaluable month (that is, at least one of the three 28-day periods has at least 14 non-missing e-diary entries; see Section 9.1.1). This population will be used to summarize the primary and other efficacy data. Patients will be analyzed according to randomized treatment assignment.

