### 10.2. Extent of Exposure

Duration of exposure will be calculated and summarized with descriptive statistics. The duration of exposure will be the date of last dose – date of the first dose +1, based on the first and last doses as recorded on the CRF.

Exposure days (number of days on study drug) is defined as the total number days reported in the diary that the patient took study drug. If the first dose date or last dose date from the CRF is not among the diary-reported dates, that day is added to the tally.

The duration of exposure and exposure days will be tabulated with summary statistics by treatment group. Additionally, the number of patients with duration of exposure by weeks ( $\leq 4$  weeks, 4 to  $\leq 8$ , 8 to  $\leq 12$ , and  $>12$  weeks) will be presented.

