a An Early Termination Visit will be conducted approximately 7 days (+3 days) of withdrawing from study

b Follow-up visit will be conducted approximately 14 days (+ 4 days) after Visit 5

c Record any changes to the medication history obtained at Screening

d Nasal exam will only be performed at Visit 6 if any abnormality on exam at Visit 5 or any report of a nasal cavity AE

e Chemistry panel only: triggered serum osmolality will be measured from same specimen if sodium is below the lower limit of normal

f Urinalyses, hematology and chemistry labs will only be repeated at Visit 6 if clinically significant findings were observed at Visit 5

g Women of childbearing potential only: screening serum pregnancy test will be analyzed at Central laboratory; consecutive urine pregnancy tests will be conducted on-site at every subsequent study visit

h Urine drug test: cocaine, phencyclidine (PCP), barbiturates, amphetamines, cannabis, and opiates

Page 42 of 51

Version Date: 2023-11-16

Version: 1.0

Tonix Pharmaceuticals  
Statistical Analysis Plan: TNX-OX-CM201

- i C-SSRS: Columbia Suicide Severity Rating Scale
- j MSI-BPD: McLean Screening Instrument for Borderline Personality Disorder
- k E-diary training will be conducted at Visit 1 (Screening Visit) and Visit 2 (Treatment) and will be repeated at Visits 3 and 4. E-diary is collected at Visit 5.
- l Patients will start completing their e-diary the day after their Screening Visit.
- m Study drug administration training performed at Visit 2 in addition to dispensation of study drug
- n PGIC: Patient Global Impression of Change
- o HADS: Hospital Anxiety and Depression Scale
- p MIDAS: Migraine Disability Assessment questionnaire
- q MSQ: Migraine-Specific Quality of Life Questionnaire v2.1
- r CSFQ-14: Changes in Sexual Functioning Questionnaire Short-Form
- s Pharmacogenomics should be drawn at Baseline but if it is not drawn, drawing at a subsequent visit is allowed.

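### SAP 7.3 scores unanswered diary days, and days between the last dose and diary collection, as missed doses, so the compliance figure mixes diary completion and visit timing with drug-taking

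*SAP*

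**What the plan says.** SAP 7.3 rules out any other source for dosing compliance: "No direct measures of drug compliance will be captured via drug accountability". This is so although return of study drug and accountability are in the visit schedule. On the period covered it says: "Compliance via the diary will be reported for the post-baseline period".

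The numerator is the number of 'Yes' answers to the morning-dose and evening-dose questions, "out of the total number of expected doses based on the dates the diary was issued and collected times 2 doses/day". The result is summarised with descriptive statistics and in four bands: below 70%, 70 to <80%, 80 to <90%, and 90 to 100%. The section has no rule for a day on which the dosing questions are unanswered, and nothing ends the count at the last dose. It reports diary completion separately, counting a day as complete if any data were entered.

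SAP 15.1 (footnote k) places collection of the e-diary at Visit 5, which is also the early termination (ET) visit. On timing, footnote a says: "An Early Termination Visit will be conducted approximately 7 days (+3 days) of withdrawing from study". The protocol (Synopsis and 4.4) instead puts the visit within 7 days of withdrawal. Protocol 8.6 prefers that it take place before a substantial gap in drug use.

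SAP 10.2 takes duration of exposure from the first and last dose dates on the CRF. It defines exposure days as "the total number days reported in the diary that the patient took study drug", and adds the first or last CRF dose date if the diary lacks it.

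**The concern.** The numerator and denominator cover different days. A dose enters the numerator only if its diary question was answered. The denominator grows by two for every calendar day until the diary is collected. Two kinds of day are then scored as non-adherence without any evidence that a due dose was missed:

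- days in the dosing period with no dosing answer, where the dose may or may not have been taken;
- days after a patient has withdrawn and before the ET visit, when no dose was due.

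The exposure-days count in SAP 10.2 has the first problem too, apart from the two CRF dates that it adds back.

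At stake is how the adherence table can be read. If the trial shows no effect, the natural question is whether patients took the spray. This is the only dosing-compliance measure planned, and it cannot separate untaken drug from unanswered diaries or a late ET visit.

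**Working it through.** The documents give no compliance figure, so there is nothing to reproduce. The check applies the SAP 7.3 formula to patients who took every dose while on drug.

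**Inputs**
- Treatment period: 84 days, so 84 × 2 = 168 expected doses (Protocol Synopsis).
- Diary floor for randomization: "entries (at least 23 days out of the 28-day period" (Protocol Synopsis, Eligibility Criteria for Randomization).
- Diary floor for an evaluable month: "at least one of the three 28-day periods has at least 14 non-missing e-diary entries" (SAP 4.2).
- Lag from last dose to diary collection: not given directly. I assume that last dose and withdrawal fall on the same day, and use 0, 3, 7 and 10 days to span both timing statements for the ET visit.

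**Formula:** score = 'Yes' answers / (2 × days from start of dosing to diary collection).

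**Unanswered days.** All 168 doses taken, dosing questions answered on d of 84 days: score = 2d/168 = d/84.
- 23 of 28 days throughout (d = 69): 138/168 = 82.1%, band 80 to <90%.
- 8 blank days (d = 76): 152/168 = 90.5%, still in the top band.
- 9 blank days (d = 75): 150/168 = 89.3%, out of the top band.
- 26 blank days (d = 58): 116/168 = 69.0%, bottom band.
- 14 of 28 days in every month (d = 42): 84/168 = 50.0%, bottom band.

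**Days after stopping.** Complete diary, every dose taken up to stop day s, diary collected g days later: score = 2s/[2(s + g)] = s/(s + g).

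| Stop day | g = 0 | g = 3 | g = 7 | g = 10 |
|---|---|---|---|---|
| 20 | 100% | 20/23 = 87.0% | 20/27 = 74.1% | 20/30 = 66.7% |
| 28 | 100% | 28/31 = 90.3% | 28/35 = 80.0% | 28/38 = 73.7% |
| 56 | 100% | 56/59 = 94.9% | 56/63 = 88.9% | 56/66 = 84.8% |

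The score leaves the top band when s/(s + g) < 0.9, that is, when s < 9g: before Day 27 for a 3-day lag and before Day 63 for a 7-day lag.

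**Both together.** Stop on Day 28, dosing answers on 23 of those 28 days, collection 7 days later: 46/(2 × 35) = 46/70 = 65.7%. Counting only to the last dose gives 46/(2 × 28) = 46/56 = 82.1%, with 10 doses unanswered. Using answered doses only gives 46/46 = 100%. The step from 65.7% to 82.1% is visit timing; the step from 82.1% to 100% is diary completion.

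**The case against.** The strongest reply is that scoring an unanswered dose as not taken is a familiar conservative convention. The SAP treats missing responder data the same way (5.2, 9.1.4.2). Patients who skip the diary may also skip the spray, and false 'Yes' answers push the score up. A reader might infer that adherence is understated overall. The documents do not support that, because the direction of the net error against true intake is unknown. This part of the reply stands, and it is why the conservative line should be kept. It does not cover days after withdrawal, and SAP 7.3 does not state the convention.

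Second, the examples can be made too severe. The 23/28 and 14/28 figures are floors, and the mITT rule needs 14 answered days in only one of three months. Protocol 6.8.5.3 provides reminders and site contact after missed entries. An ET visit within 7 days, or before a gap in dosing, means a short lag or none, so a reader should not assume 7 to 10 days for every early stopper. The study schema expects about 265 of 300 to complete, so the lag concerns about 35/300 = 12% of patients. All of this stands.

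Third, diary completion (SAP 7.3) and CRF duration of exposure (SAP 10.2) are also reported, so the compliance table is not the only evidence. That helps, but it does not allow an exact correction. A day with headache answers and blank dosing questions counts as a completed diary day and as two missed doses.

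Finally, a reader might infer that the count starts when the diary app is set up at Visit 1, which with a 28-day run-in would give perfect dosing 84/112 = 75%. The restriction to the post-baseline period argues against that reading, and the point here does not rest on it.

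**Conclusion.** The point holds as a defect in the definition of a descriptive measure. Under SAP 7.3 as written, the score is a lower bound on doses taken, provided that the 'Yes' answers are accurate. It also mixes in diary completion and the timing of the ET visit. Its size for a fully adherent patient follows the arithmetic above: nothing with a complete diary and no lag, about 18 percentage points at 23/28 completion, and 0 to 33 points for a Day 20 stop with a lag of 0 to 10 days. The size across the trial cannot be given, because the documents contain neither diary completion nor stopping times.

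A reader might also infer a false difference in adherence between arms. That would need diary completion, withdrawal or visit lag to differ by arm, and the documents give no evidence on this. No analysis population, estimand or efficacy test uses the score, so the trial's inference is untouched. This is a small clarification, worth making because it uses data already collected.

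**What to change.** In SAP 7.3:

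- Define expected doses as two per day from the CRF first dose date to the CRF last dose date, allowing for part days. For example, a completer who takes only the morning dose on Day 85 would otherwise score at most 169/170 = 99.4%.
- Keep 'unanswered = not taken' over that window as the main line and for the bands, and say that it is deliberate.
- Report the number of unanswered doses separately from 'No' answers.
- Add one line with answered doses only. It serves as the upper bound if patients take the drug no more often on unanswered days than on answered ones.

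In SAP 10.2, show exposure days beside the number of days with an answered dosing question.

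The cost is SAP wording and one or two table rows, with no new data. There are two downsides. The answered-only line can overstate adherence if patients skip the diary when they skip the drug: someone who answers on 10 of 84 days, all 'Yes', scores 20/20 = 100% there against 20/168 = 11.9% on the main line, so both must be shown. And ending the window at the last dose means that a patient who stops the drug but stays in the study is no longer penalised here. That has to be read from duration of exposure in SAP 10.2, and the table should refer to it.
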